9.0 Procedures Involved

9.1 Procedures for provider focus groups/ patient interviews. [name] (who is experienced in leading clinician-based focus groups) will lead all

PROTOCOL TITLE:

clinician focus groups. All patient focus group and phone interviews will be led by a trained qualitative researcher, [name], or a trained CRC from the DFCI Survey and Data Management Core ('Core'). All discussions will be recorded and professionally transcribed. The Core is a very experienced and well-established team that readily organizes and facilitates focus groups and performs qualitative data analyses. They have a long track record of successful and effective work in this area and their expertise will also be utilized to adapt the communication tool at completion of this qualitative aim. At the start of the clinician focus groups, verbal consent from each participant will be obtained. For patients (who are interviewed by phone), a waiver of written consent will be requested and verbal consent will be obtained. Patients will undergo a brief cognitive function (Blessed Orientation-Memory-Concentration test [BOMC])⁷³ and capacity evaluation (Appendix A) and will proceed with the interview if they score <10 points on the BOMC and answer ≥ 4 capacity questions correctly.

- 9.2 Discussion Content. Clinicians will be asked to comment on (a) the panel recommendations from DFCI OHRS exempt protocol 18-526, (b) how they currently talk with patients about surveillance and whether and how they might incorporate risk or life expectancy in conversations, (c) the draft communication tool (including exploring whether electronic tools appeal to clinicians), and (d) ideal communication strategies for PCs and oncologists to coordinate follow-up care. Patients will first be asked a short series of discrete questions which will be followed by discussion of topics focused on the patient experience and comfort in hearing information about life expectancy, whether they have ever discussed cessation of mammography, and their preferences for receiving the information presented on the communication tool (mailed to them ahead of time). We will also inquire about whether electronic versions of the tool might appeal to patients and clinicians or whether they prefer paper versions. Draft scripts for clinician and patient focus group and phone interviews are provided in Appendix C. These will be amended as appropriate before initiation of this component of the study.
- 9.3 Survey Instruments. The draft 'pre'/'post' patient surveys and a post-visit clinician survey (all three draft surveys) are in Appendix D. Surveys contain closed-ended questions (except for solicited comments at the end) and are adapted from [name] prior, validated surveys conducted before and after the use of a decision aid for screening mammography in older women.⁶⁶ We will ask about demographics, health literacy and numeracy ('pre' patient), mammography intentions ('pre' and 'post' patient), mammography knowledge ('pre' and 'post' patient), anxiety about recurrence ('pre' patient), acceptability of the communication tool ('pre' patient and clinician), comfort level and interest in discussions about life expectancy ('pre' and 'post' patient and clinician), decisional

PROTOCOL TITLE:

conflict ('pre' and 'post' patient), preferences for a paper/online tool ('post' patient and clinician), and time added to appointments ('post' clinician).

10.0 Data and Specimen Banking – there is no specimen banking as part of this protocol

11.0 Data Management and Confidentiality

11.1 The data analysis plan and procedures are described in Section 8.

11.2 Data Management Plan: We will use a secure, password-protected REDCap database to capture information for the intervention part of this study (Aim 1.2). Data elements to be included in the centralized study data repository will include baseline demographics, comorbidity, medications, date of diagnosis, disease characteristics, and survey information. All survey data will be specifically entered and maintained securely in password protected systems.

All study components will be run from Dana-Farber Cancer Institute. Study staff will computerize the data from the patient questionnaires in this observational study. In addition, study staff will computerize medical information on each of the study participants into the centralized, secure database. For patients invited into the study but who choose not to participate, there will be no retention of patient identifiers. Study staff will record the age, race, date of diagnosis and surgery for all patients who decline participation to allow for demographic comparison of participants and nonparticipants. All original copies of data will be kept in file cabinet locked in study staff offices. Computerized databases will be password protected. Data will be collected, coded, and managed by study staff only. The name and address file will be stored on a separate computer with password protection from the data files to protect the identity of respondents. Data and software will be backed up on a nightly basis as per our institutional norm.

11.3 Data Security. All data files will be stored on password-protected, secure servers. Access to the data will be limited to members of the research team. All patient names and contact information will be kept strictly confidential in a password-protected file stored separately at each study site, separate from the survey and medical record data. The survey/medical record data files will contain the CASE ID only, a unique study identification number, and only that number will be included in analytic databases shared by team members. Patient contact information will be stored in a separate password-protected database, for use by the study team only. This list will be used only for tracking potential participants, specifically for documenting attempts to reach patients. A separate password-protected file containing the crosswalk between the patient name and unique ID will be maintained

PROTOCOL TITLE:

separately. Upon enrolling a patient, the study staff will use the unique study ID and will enter survey responses directly into the database from the computer interface. All answers to survey questions will be linked with the case ID only and no identifying information.

11.4 The study protocol will strictly adhere to all HIPAA and Dana-Farber regulations. Confidentiality of the subjects will be maintained. The study team will be utilizing standard clinical workflows and may involve virtual substitution of office visits such as the use of Zoom Video Communications application. Although in-person office visits are preferred on site, virtual visits via Zoom conferences, which are HIPPA compliant and protected, can provide a safer and efficient alternative for patients. No data will be linked to a particular name or personal identifiers. The individual results will not be disclosed. The de-identified dataset will be provided to the investigators for analysis. The composite results will be analyzed and summarized for presentation and publication. We will minimize risks regarding confidentiality by strictly following the practices described above.

12.0 Provisions to Monitor the Data to Ensure the Safety of Subjects

This is not a therapeutic intervention study. If a patient notes distress or physical concerns, we will immediately notify her treatment team.

13.0 Withdrawal of Subjects

Patients may withdraw at any time if they wish to end their involvement of the study.

14.0 Risks to Subjects

We anticipate that this study will entail minimal physical and psychological risk on the part of the subjects. In the letter of introduction and in verbal consent, patients will be advised to contact their physicians or a study representative with any questions or concerns. Individual patient results will be kept confidential. As with any collection of individually identifiable health information, there is a risk of breach of confidentiality. However, adequate safeguards will be in place to ensure that these risks are minimized, including the following measures described below.

15.0 Potential Benefits to Subjects

There are no direct benefits to study participants, but the study team will show our appreciation for study enrollment with gift cards as described. We hope that patients will be satisfied with having participated in and contributed to a study where there is great need for prospective data.

16.0 Vulnerable Populations

We aim to include older patients, a vulnerable patient group who is in urgent need of more prospective evidence to guide their care. We also aim to have a diverse sample by socioeconomic and race/ethnicity factors.

PROTOCOL TITLE:

17.0 Community-Based Participatory Research

For optimal generalizability, we are working with DFCI, DFCI at South Shore Hospital, DFCI at St. Elizabeth's, and Brigham and Women's Hospital primary care physicians and geriatricians on this project. We will also have a virtual component for providers so that we get input from providers outside of Boston. We aim to be very inclusive of providers caring for patients in our study including primary care providers and oncologists.

18.0 Sharing of Results with Subjects

We will not directly share results with patients but they will be widely available once published and disseminated..

19.0 Setting

See sections above- this study will take place at DFCI main campus/St. Elizabeth's/South Shore Hospital, Brigham and Women's Hospital,, and on the phone/virtually, depending on the study component.

20.0 Resources Available

[name] (along with her collaborators) is well poised to execute the proposed research focusing on older breast cancer patients because of her training, expertise, and experiences as a clinician-researcher focused in this area of study. The work planned in this study logically builds on her prior work and on the prior work of her study collaborators. [name] will have all of the resources available to her at DFCI for the duration of this study, including statistical, research, and nursing support in addition to grants support and the support of the collaborating institutions participating in this work (DFCI satellites and affiliates).

21.0 Prior Approvals – N/A

22.0 Recruitment Methods – See Section 5

23.0 Local Number of Subjects- See Section 4

24.0 Provisions to Protect the Privacy Interests of Subjects

Study staff will obtain permission from the primary medical oncologist before contacting potential subjects. Only study staff who have completed institutional training and are familiar with the protocol will contact patients for an informed verbal consent. Only staff who have completed training can access Epic or other patient medical record databases. Study staff may conduct a limited review of a patient's medical record in order to confirm eligibility; they may continue to access their records.

25.0 Compensation for Research-Related Injury

This study involves Minimal Risk to subjects. Therefore, there is no compensation available to subjects in the event of research-related injury.

PROTOCOL TITLE:

26.0 Economic Burden to Subjects

We plan to approach patients when they are already at their provider visits and will call them if time point is missed in person. We do not anticipate any additional costs to patients while participating in this study. Participants are given gift cards for their time.

27.0 Consent Process

All participating patients (interviews) and providers (focus groups) will provide informed verbal informed consent at the start of their interview/focus group (Appendix E). All participating patients for Aim 1.2 (pilot intervention) will provide verbal informed consent (Appendix F) before any study procedures are performed. Patients and providers will receive a copy of their verbal consent. Ethical standards for human subjects will be strictly followed. We will not obtain written consent as it is practically prohibitive for this short survey-based intervention. The consent script will include all required information commonly included on signed consent forms. Moreover, the participant will explicitly be asked if he or she consents to participate prior to commencing the survey.

All investigators and research assistants will have undergone full training in Human Subjects Protection Certification. In addition, all research team members will undergo formal training regarding the research procedures, including the informed consent process. The purpose, procedures, duration, risks, and alternatives of the study will be explained to potential subjects. It will be emphasized in the verbal consent that participation is completely voluntary and that patients may choose to withdraw at any time without adverse consequence to their medical care or loss of benefits to which they are otherwise entitled. Patients will be informed of the research nature of this project. Extent of confidentiality provided and procedures for protecting confidentiality will be discussed in specifics, such as the need to review medical records to confirm cancer treatments. Informed verbal consent will be contingent upon the patient's full awareness and affirmation of these ethical standards. Once all questions have been addressed and the individual indicates she would like to participate, informed consent will be obtained. Individuals who are unable to provide informed consent will be excluded from participation in the study.

28.0 Process to Document Consent in Writing

28.1 Because this research presents no more than minimal risk of harm to subjects and involves no procedures for which written documentation of consent is normally required outside of the research context, we waive the requirement to obtain written documentation of consent as noted above.

APPENDIX A
Blessed Orientation-Memory Concentration Test

Cognition: Orientation-Memory-Concentration Test⁷³

IV) Cognition: Orientation-Memory-Concentration Test					
	Patient's response	Maximum errors	Score	Weight	Final Score
1. What year is it now? [without looking at a calendar]	   	1		x 4 =	
2. What month is it now? [without looking at a calendar]	 	1		x 3 =	
Memory phrase					
Repeat this phrase after me: 'John Brown, 42 Market Street, Chicago.'					
3. About what time is it?[within 1 hour - without looking at your watch]	  :  	1		x 3 =	
4. Count backwards from 20 to 1.		2		x 2 =	
5. Say the months in reverse order.		2		x 2 =	
6. Repeat the memory phrase.		5		x 2 =	 
Total Score =					 

Scoring: For items 1 to 3, the response is either correct (score 0) or incorrect (score 1). For items 4 to 6, subtract one point for each error (item 4 and 5 maximum error is 2; for item 6, maximum error is 5); total all scores in "Final Score" column. Total score of 11 or greater indicates cognitive impairment; please notify MD and assist patient in completing questionnaires. Maximum score = 28
					

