****START RECORDING****

We are working on strategies to better tailor follow up care for women aged 75 and older who have a history of breast cancer. We are a deeply interested in understanding patients' perspectives about how doctors and patients can work together to make decisions about follow up care. In the mail, you should have received a packet. Please keep this packet with you during our conversation. We will have you open the seal on it during our interview, a bit later on.

PART B

BACKGROUND QUESTIONNAIRE (10 minutes)

We will first ask you a series of questions that help us learn about you and your cancer history.

1. Orientation-Memory-Concentration Test Short Blessed Test (SDT) – Scores filled in by interviewer (<http://geriatrictoolkit.missouri.edu/cog/bomc.pdf>)- Entire Part B is for patient one-on-one interviews only

Question	Maximum Error	Score X	Weight
What year is it now?	1	x 4	=
What month is it now? Repeat this phrase and I will ask you to remember it and tell it to me later: John Brown, 42 Market Street, Chicago	1	___ x 3	= ___
About what time is it? (within one hour)	1	___ x 3	= ___
Count backwards 20 to 1	2	x 2	=
Say the months in reverse order	2	x 2	=
Repeat the phrase just given	5	___ x 2	= ___
Total error score = _____			

(If patient scores ≥ 10 , she is ineligible. Thank her for her time, let her know she is not eligible)

We will next ask you about your breast cancer and current follow up plan.

2. When was your breast cancer diagnosed?
- Less than one year ago
 - More than one but less than 2 years ago
 - Between 2 and 5 years ago
 - More than 5 years ago
 - Not sure

PROTOCOL TITLE:

3. Do you still see a medical oncologist or a nurse practitioner/physician assistant in the medical oncologist's office regularly?
 - Yes → If yes, how often?
 - No → If no, when was the last time you had follow up with your medical oncologist?
 - Not sure
4. Do you still see a surgical oncologist or an NP/PA in their office?
 - Yes → If yes, how often?
 - No → If no, when was the last time you had follow up in your surgeon's office?
5. Do you see anyone else for follow up of your cancer?
 - Yes → who?
 - No
 - Not sure
6. Does your primary care provider discuss your breast cancer history with you regularly?
 - Yes
 - No
 - Not sure
 - Other _____
7. Do you still get mammograms?
 - Yes → If yes, when was your last mammogram? → Who typically orders your mammograms? (Oncologist, PCP, someone else?)
 - No → If no, when was your last mammogram?

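### Appendix A says to subtract errors on items 4 to 6 of the cognitive screen, but the instrument only works if they are added (minor; the Appendix C grid scores correctly)

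*Protocol*

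**What the plan says.** Sections 5.1 and 9.1 of the protocol make two things necessary before a one-on-one phone interview goes ahead: fewer than 10 points on the Blessed Orientation-Memory-Concentration test, and at least four capacity questions answered correctly. Both sections point to Appendix A for this evaluation.

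Appendix A is a six-item form with columns for "Maximum errors", score, weight and final score. Items 1 to 3 score 0 if right and 1 if wrong. For the rest, the instruction is "For items 4 to 6, subtract one point for each error". The final scores are then totalled. A total of 11 or more "indicates cognitive impairment; please notify MD and assist patient in completing questionnaires", and the form closes with "Maximum score = 28".

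Appendix C, the draft patient script, has its own grid with the same items, error limits and weights. It is marked "Scores filled in by interviewer" and "Entire Part B is for patient one-on-one interviews only", and its sum is labelled "Total error score". At 10 or more, "she is ineligible. Thank her for her time, let her know she is not eligible".

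**The concern.** The appendix that the protocol body names for the screen tells the scorer to move items 4 to 6 in the opposite direction from items 1 to 3. Items 4 to 6 carry 18 of the 28 available points, so the direction matters. Anyone who scored from the Appendix A text alone would get a wrong total and compare it with a cut-off of 10 that assumes added errors. Depending on how the instruction was understood, a woman with marked impairment could meet the score condition, or a woman with a perfect performance could be turned away. The screen comes before a conversation that touches on life expectancy with mostly older women, so it should admit and exclude the right people.

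**Working it through.** **Inputs (Appendix A grid; Appendix C has the same values).** Maximum errors for items 1 to 6: 1, 1, 1, 2, 2, 5. Weights: 4, 3, 3, 2, 2, 2. Let *f* be the weighted errors on items 1 to 3 (0 to 10) and *l* the weighted errors on items 4 to 6 (0 to 18).

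**Step 1. Reproduce the stated maximum by adding.** Total = *f* + *l*. The maximum is 1×4 + 1×3 + 1×3 + 2×2 + 2×2 + 5×2 = 4 + 3 + 3 + 4 + 4 + 10 = 28, as Appendix A states. The minimum is 0.

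**Step 2. Errors as negative points.** Total = *f* − *l*. The maximum is 10 − 0 = 10 and the minimum is 0 − 18 = −18. A woman wrong on everything scores 10 − 18 = −8. No total can reach 11, so the form could never label anyone impaired.

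**Step 3. Errors taken off full credit.** Full credit on items 4 to 6 is 4 + 4 + 10 = 18, so total = *f* + 18 − *l*. The range is 0 to 28. A woman with no errors scores 0 + 18 − 0 = 18.

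| Performance | Add | Negative points | Off full credit |
|---|---|---|---|
| No errors | 0 | 0 | 18 |
| Only items 1 to 3 wrong | 10 | 10 | 28 |
| Only items 4 to 6 wrong, all errors | 18 | −18 | 0 |
| Everything wrong | 28 | −8 | 10 |

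**Step 4. Which features decide between the readings.** The maximum of 28 rules out step 2, whose maximum is 10. It does not rule out step 3, which also peaks at 28. What rules out step 3 is the error scoring of items 1 to 3, the reading of a high total as impairment (a flawless performance would be labelled impaired at 18), and the error total in Appendix C. Only addition fits everything.

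**Step 5. How far the score condition is disturbed.** There are 2×2×2×3×3×6 = 432 possible error patterns. By addition, 347 score 10 or more and 432 − 347 = 85 score below 10.

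- *Negative points:* reaching 10 requires *f* = 10 and *l* = 0, which is one pattern. So 347 − 1 = 346 patterns that should fail the score condition would meet it.
- *Off full credit:* a total below 10 requires *l* − *f* > 8. Since *l* is even, *l* must be at least 10, and then *f* + *l* is also at least 10. So none of the 85 patterns that should pass scores below 10. By enumeration, 85 of the 347 that should fail do.

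These are counts of patterns, each weighted equally. They are not estimates of how many women would be affected, and they concern only the first of the two conditions in Sections 5.1 and 9.1.

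**The case against.** The strongest reply is that the form corrects itself and that the step is not performed from Appendix A's prose anyway. The grid multiplies a positive error count by a positive weight, and a high total means impairment. The interviewer fills in the Appendix C grid, which is right and states the cut-off. Interviewers are trained, and a negative total or an 18 for a perfect performance would probably be noticed. Even a woman wrongly passed on the score must still answer at least four capacity questions correctly, and Section 3 excludes patients who are unable to consent. All of this stands, and it is why the point is minor. It does not make the instruction correct.

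A reader might infer three further things that the documents do not support.

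- *That the stated maximum of 28 by itself proves addition.* It does not, because subtraction from full credit also peaks at 28. The case rests on the other features in step 4.
- *That 11 in Appendix A competes with 10 elsewhere as an eligibility rule.* The 11 is the form's label for impairment. The eligibility rule is below 10 in Sections 5.1 and 9.1, with 10 or more ineligible in Appendix C.
- *That the script contradicts Appendix A on notifying the clinician.* The script says what to tell the woman and is silent on notification. It is a draft that Section 9.2 expects to be amended, and silence there is not a conflict.

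**Conclusion.** Wrong as written, and minor. The scoring sentence for items 4 to 6 in Appendix A has the wrong verb: errors are added, on a scale of 0 to 28. Taken literally, either form of subtraction undoes the screen: one gives -8 to a woman who fails everything, the other 18 to a woman who makes no error.

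A reader might go further and conclude that impaired women would be interviewed, or suitable women excluded, in any number. The documents do not show that. They provide a correct grid for the interviewer and a second condition to pass, and they give no indication of how many women, if any, would be scored from Appendix A's text. Exposure is limited to the one-on-one phone interviews in Aim 1.1, which are some of up to 30 patients in a qualitative component. No Aim 1.2 outcome and no analysis in the SAP uses the test.

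That the error has a small effect assumes that interviewers use the Appendix C grid as scripted. That the wording is wrong depends on no such assumption.

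**What to change.** In Appendix A, change *subtract* to *add* for items 4 to 6. Add a note that study eligibility requires a score below 10, as Sections 5.1 and 9.1 and Appendix C already state, so the advice to help the patient with questionnaires does not apply to a woman scoring 10 or more. Leave the impairment label at 11 or more and its instruction to notify the physician as they are, and add no notification line to the script.

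The cost is one word and one note in a single appendix. Sample size, endpoints, analysis and the interviewer's grid do not change.
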